Cover Page for ClinicalTrials.gov

Official Title of the Study:

Trauma-Focused Equine-Assisted Therapy (TF-EAT) for Veterans With PTSD

NCT Number:

NCT03068325

Principal Investigator:

[name]

[contact]

[contact]

Date of Document:

February 9, 2022

Statistical Analysis Plan

The Little MCAR (missing completely at random) test on total scores for the CAPS-5, PCL-5, HDRS, and BDI-II from each time point following the baseline assessment (i.e., midpoint, posttreatment, and follow-up analysis) will be used to test whether data is missing at random.

In line with previous open-trial studies exploring novel psychotherapies for different psychopathologies, we will use an intent-to-treat analysis, thereby enabling data analysis for all 63 patients. Provided that missing data is minimal and missing at random, we will conduct the intent-to-treat analysis with full information maximum likelihood (FIML), a gold standard approach to handling missing data. In addition, we will repeat analyses for patients who complete assessments at all four time points. Treatment effects will be explored using a repeated-measures analysis of variance (ANOVA) with time (pretreatment, midpoint, posttreatment, and follow-up) as a within-subjects factor. Post hoc tests using the Bonferroni correction will be used to compare the different time points. All statistical tests will be 2-sided, using $\alpha \leq .05$. Effect sizes will be reported using η^2 and Cohen d when appropriate.

Protocol Title: **Trauma-Focused Equine-Assisted Treatment (TF-EAT) for Veterans with PTSD**

Version Date:
02/09/2022

Protocol Number:
7232

First Approval:
03/11/2016

Expiration Date:
02/21/2023

Contact Principal Investigator:
[name], PHD
Email: [contact]
[contact]

Co-Investigator(s):
[name]
[name], PHD

Research Chief:
[name]

Cover Sheet

Choose **ONE** option from the following that is applicable to your study
If you are creating a new protocol, select "I am submitting a new protocol." As 5 Year Renewals are no longer required, this option remains for historical purposes.
I am submitting an annual continuation without modifications

Department & Unaffiliated Personnel

Department

What Department does the PI belong to?
Clinical Therapeutics
Within the department, what Center or group are you affiliated with, if any?
Anxiety Disorders Clinic

Unaffiliated Personnel

List investigators, if any, who will be participating in this protocol but are not affiliated with New York

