In this pilot study we will further develop the TF-EAT intervention and determine whether research methods (evaluation interviews, assessment measures, videotaping procedures etc.) are acceptable to participants. An open trial of this intervention and the draft manual will be finalized in Phase 1 and evaluated in Phase 2. Specifically, we will focus on issues such as session length, appropriateness of the “content” for treatment of PTSD, ordering of session content, adherence to the intention of the manual of the equine therapeutic team (based on observations made during supervision and feedback from the consultants), and will detail logistics of data collection and how best to record the sessions (camera angles, etc.). We will conduct 2 groups of 4-6 participants for Phase 1 and 6 groups of 4-6 participants for Phase 2.

Description of Subject Population

Sample #1

Specify subject population

Veterans

Number of completers required to accomplish study aims

60

Projected number of subjects who will be enrolled to obtain required number of completers

70

Age range of subject population
18-75

Gender, Racial and Ethnic Breakdown

Gender:
10% female
90% male

Ethnicity:
15% Hispanic
60% White
15% African-American
10% Other.

Description of subject population

All patients will have DSM-5 diagnosis of PTSD. The expected sex and ethnicity distributions are based on population data drawn from the VA.

Recruitment Procedures

Describe settings where recruitment will occur

Anxiety Disorders Clinic

How and by whom will subjects be approached and/or recruited?

Patients will respond to an advertisement (see below " study advertised/ publicized"). Patient will call the clinic and after verbal consent is obtained the research assistant (RA) will conduct a preliminary phone screen that is part of a preexisting screening protocol (IRB # 7094R). If the patient will be eligible for the study the RA will invite him for further screening at the clinic. Current or prospective patients of the Columbia Veterans Research Center (IRB #7218) may also be referred for this treatment study as appropriate.

How will the study be advertised/publicized?

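### Bonferroni is valid for the post hoc time comparisons, but Holm's step-down procedure keeps the same 5% familywise bound and can only add rejections; the gain is anywhere from nil to material, depending on the symptom course

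*Combined protocol and SAP*

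**What the plan says.** The Statistical Analysis Plan section fits a repeated-measures ANOVA with "time (pretreatment, midpoint, posttreatment, and follow-up) as a within-subjects factor". It then states: "Post hoc tests using the Bonferroni correction will be used to compare the different time points". On error rates it adds "All statistical tests will be 2-sided", at a level of .05. The intent-to-treat analysis covers the whole trial sample, "thereby enabling data analysis for all 63 patients", and for completers "we will repeat analyses for patients who complete assessments at all four time points".

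The section does not list the pairs to be compared, give a reason for single-step Bonferroni, or mention a step-down method. Neither it nor the protocol gives a planning effect size, a within-patient correlation or a target power.

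On timing, the Application for Continuation of Research reports that all interventions are finished and only data analysis remains. Its summary of experiences to date lists one published open-trial paper. The document is dated February 9, 2022.

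**The concern.** Single-step Bonferroni holds every pair to the strictest threshold, however many other pairs have already been rejected. Holm relaxes the threshold after each rejection and needs no further assumption about how the tests are correlated. A large improvement from pretreatment will usually be rejected first, so the relaxation helps the smaller contrasts: midpoint versus posttreatment, and posttreatment versus follow-up.

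Those contrasts bear on whether patients keep improving in the second half of treatment and whether they lose ground in the three months afterwards. If power for posttreatment versus follow-up is low, a non-significant result may be read as evidence that gains were maintained.

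**Working it through.** **Inputs.** From the Statistical Analysis Plan: four time points, two-sided .05, n = 63. Inferred: all pairs are compared, and .05 is the familywise level within each outcome. Assumed, because the documents are silent: mean profiles in baseline SD units, equal variances, and a common within-patient correlation. The plan has no power figure to reproduce.

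**Thresholds.** Number of pairs = 4 × 3 / 2 = 6. Bonferroni tests every pair at .05/6 = .0083. Holm tests the i-th smallest p-value at .05/(6 − i + 1), which gives .0083, .0100, .0125, .0167, .0250 and .0500, and stops at the first failure. No Holm threshold is below .0083, so Holm cannot lose a Bonferroni rejection. The first thresholds are equal, so the chance of at least one rejection is the same under both.

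**Limits of the gain for one contrast.** For a paired t test with n = 63, the standardised effect (mean difference over SD of differences) detectable with 80% power is 0.451 at .0083 and 0.359 at .05. For an effect of 0.3, power is 37% at .0083 and 65% at .05, so Holm can add at most 65 − 37 = 28 points.

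**From SD units to the paired effect.** Paired effect = difference / √(2(1 − ρ)). With ρ = 0.6 and a difference of 0.3 SD, this is 0.3/√0.8 = 0.335. The noncentrality is 0.335 × √63 = 2.66, which gives about 48% power at .0083, in line with the simulation.

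**Simulation.** Six paired t tests, n = 63, ρ = 0.6, 40,000 trials per profile. Power (%) is shown as Bonferroni → Holm.

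| Means at pre, mid, post, follow-up (SD) | Pre–mid | Pre–post | Pre–follow-up | Mid–post | Mid–follow-up | Post–follow-up |
|---|---|---|---|---|---|---|
| 0, −0.5, −0.8, −0.5 | 95.2 → 97.6 | 100 → 100 | 95.3 → 97.8 | 48.0 → 61.3 | no true difference | 47.9 → 61.4 |
| 0, −0.4, −0.7, −0.45 | 79.0 → 86.3 | 100 → 100 | 89.2 → 93.1 | 48.0 → 59.4 | 1.5 → 3.7 | 31.6 → 43.9 |
| 0, −0.6, −0.7, −0.65 | 99.4 → 99.7 | 100 → 100 | 99.8 → 99.9 | 4.0 → 7.0 | 1.5 → 3.1 | 1.5 → 3.1 |
| 0, −0.2, −0.3, −0.25 | 18.4 → 20.8 | 48.2 → 49.5 | 31.9 → 34.2 | 4.0 → 5.0 | 1.5 → 2.1 | 1.5 → 1.9 |
| 0, −0.8, −0.8, −0.8 | 100 → 100 | 100 → 100 | 100 → 100 | no true difference | no true difference | no true difference |

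Holm lost no Bonferroni rejection in any simulated trial. In the first two profiles about 30% of trials gained at least one rejection.

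**Sensitivity.** With an assumed 50 completers, posttreatment versus follow-up rises from 36.5% to 48.8% in the first profile and from 23.2% to 32.7% in the second. The largest gain seen in any profile was for posttreatment versus follow-up with means 0, −0.5, −1.0, −0.8 and ρ = 0.7: 26% to 50%.

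**Familywise error.** With no true differences it is 4.3% under both methods. With one truly null pair (first profile) it rises from under 1% to just under 3% with Holm. With three null pairs (last profile) it rises from 2.3% to 4.5%. All stay within 5%.

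**The case against.** The best case for leaving the plan alone has four parts.

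- **Bonferroni is valid and conventional.** This stands. A reader might infer that the plan contains an error, but it does not: its familywise error is controlled. The point is efficiency only.
- **The small contrasts are not shown to be decisive.** This stands. A reader might infer that midpoint versus posttreatment and posttreatment versus follow-up determine the trial's conclusion. The Statistical Analysis Plan only explores treatment effects, and the numbered aims in the Lay Summary concern the manual, feasibility, acceptability, safety and neural changes. Whether benefit lasts is also addressed by pretreatment versus follow-up, which already has 95% and 89% power under Bonferroni in the two relapse profiles.
- **The larger gains depend on the assumed course.** This stands. Quoting 11 to 13 points as the general benefit would be wrong, because those profiles assume a marked relapse; flatter profiles give 3 points or less. The simulation also uses complete-data paired t tests, whereas the plan uses full information maximum likelihood. That affects the size of the gain but not the ordering of the two methods, since Holm works on whatever valid p-values the model supplies.
- **The switch is not free.** This stands. A reader might call Holm a replacement with no trade-off. But Holm has no simple simultaneous intervals, and the plan intends to report effect sizes. It uses more of the error allowance when some differences are truly zero. With data collection complete and a paper out, a rule that can only add significant results is a change in the favourable direction. The documents do not show which analyses have already been run.

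None of this removes the central fact that, on the same p-values and at the same 5% bound, Holm rejects at least as much.

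**Conclusion.** A minor point of efficiency. If six pairs are compared, Bonferroni gives up power that Holm would keep under the same bound. At n = 63 and ρ = 0.6, the gain for midpoint versus posttreatment and posttreatment versus follow-up runs from 0–3 points (flat or small later changes) to about 11–13 points (relapse of 0.25–0.3 SD). Other assumed profiles and a higher correlation can take posttreatment versus follow-up further, to 24 points at the extreme. Pretreatment versus posttreatment gains about 1 point at most.

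These sizes are assumptions, not properties of the trial. If the sponsor means fewer than six pairs, the loss shrinks. With three pairs, for example, Bonferroni's threshold is .05/3 = .0167, and Holm's are .0167, .0250 and .0500. Neither method, applied within an outcome, deals with multiplicity across the CAPS-5, PCL-5, HDRS and BDI-II. The documents do not support rewriting the rule for results already obtained.

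**What to change.** For analyses not yet run, replace the post hoc sentence with: *Pairwise comparisons of the time points will use Holm's step-down procedure within each outcome.* List the intended pairs in the same place, and record the date of the change and that it followed data collection.

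For results already produced under Bonferroni, leave them as reported and add Holm-adjusted p-values as a labelled post hoc sensitivity analysis. The same p-values suffice, so no new data or models are needed.

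For intervals, either keep Bonferroni intervals, at 1 − .05/6 = 99.2% for each of six pairs, or show unadjusted 95% intervals labelled as such. Say in the report that either kind may disagree with a Holm decision.

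The cost is one sentence and a footnote. The 5% bound and the set of comparisons do not change. What is given up is exact agreement between tests and simultaneous intervals, and some of Bonferroni's slack in attained familywise error.

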The sample will consist of veterans and servicemembers with PTSD (n=48) who have been assessed through the Columbia Veterans Research Center (IRB #7218), or preferred to be screened directly as a response to advertisement. In Phase 1, aiming to finalize the EAT manual, 8 veterans and servicemembers will be treated in 2 groups of 4 veterans each. Participants will be evaluated at baseline, at treatment mid-point (week 4), and at the end of treatment.

In Phase 2, where the EAT manual will continue to be evaluated, the remainder of the sample (n=40) will be treated in 6-8 groups (4-6 veterans each). Participants will be evaluated at baseline, at treatment mid-point (week 4), at end of treatment (week 8), and at three-month follow-up by independent evaluators. Additionally, patients will be scanned at baseline and end of treatment. Structural MRI scans will be performed to quantify regional brain volumes and cortical thickness, and resting state fMRI will measure functional connectivity within hippocampal networks.

Background, Significance and Rationale

Background, Significance and Rationale

Posttraumatic stress disorder (PTSD) is a debilitating disorder highly prevalent among military veterans and servicemembers. It is defined by a fearful response to traumatic events, and involves re-experiencing, hyperarousal, and avoidance of reminders of the traumatic events. While some widely practiced therapies have demonstrated efficacy for treating PTSD, for instance Prolonged Exposure therapy (PE), alternative treatment modalities offer opportunities for individuals who either do not wish to try or do not benefit from empirically validated therapies. However, alternative treatments often lack rigorous empirical justification of their treatment efficacy.

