Potential subjects will be informed of the study through: (a) referrals from the Department of Veteran Affairs, (b) word-of-mouth referrals from former subjects, (c) referrals from area medical and mental health professionals, (d) publicity about the study, including articles in local newspapers and magazines, our IRB-approved website (<http://columbiapsychiatry.org/ptsd>), IRB approved flyers, appearances on local radio and television shows, etc., leading to self-referral of prospective subjects, (e) advertisements placed in local media and on the Internet. (f) Attendance by study personnel at local veterans' events.

Do you have ads/recruitment material requiring review at this time?

Yes

Does this study involve a clinical trial?

No

Concurrent Research Studies

Will subjects in this study participate in or be recruited from other studies?

Yes

Describe concurrent research involvement

Participants may be recruited from the Columbia Veterans Research Center (IRB #7218), as well as other studies concerning PTSD conducted through our department as appropriate, such as Neural Signature of Trauma (IRB #7136).

Inclusion/Exclusion Criteria

Name the subject group/sub sample

Veterans

Create or insert table to describe the inclusion criteria and methods to ascertain them

Inclusion criteria:

1. Between ages of 18 and 75	Method of Ascertainment: History
2. Current DSM-5 diagnosis of PTSD as determined by a) full criteria met on CAPS-4, and b) clinical assessment	SCID, CAPS-4, Clinical Assessment
3. CAPS-4 score equal to or greater than 50	CAPS-4 administration
4. Able to give consent, fluent in English.	Clinical assessment, Clinical judgment
5. Prior military experience	History, Columbia Veterans Research Center Background Information Questionnaire
6. MMSE score equal to or greater than 24 (for participants over 60 years of age)	MMSE administration

Create or insert table to describe the exclusion criteria and methods to ascertain them

Exclusion criteria:

1. History of psychiatric diagnosis of psychotic disorder, unstable bipolar disorder.	Method of Ascertainment: SCID (including personality disorder modules) and clinical evaluation
2. Elevated depression of clinical concern and/or score of >25 on the Hamilton Rating Scale for Depression (HAM-D-17-item).	Clinical assessment, HAM-D 17 and BDI-II. All cases of PTSD and comorbid depression will be reviewed by PI and clinician for exclusion

	determination.

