Patient will meet face to face with a person that is authorized to discuss and document consent (see “person designed to discuss and document consent”). After patient reads the consent the clinician will go over the consent with the patient and answer all the patient’s questions. After answering all the patient’s questions by the clinician patient will sign the study consent. Throughout this process, the patient will be told that they are free to refuse to participate in the research and that participation or non-participation in research has no effect on their ability to continue to receive clinical care or services. Patients who chose not to participate in this study are still eligible for treatment in the Columbia Veterans Research Center (IRB #7218). Patients will also be asked to sign a standard liability waiver provided by the Bergen Equestrian Center (Attached).

Indicate which of the following are employed as a part of screening or main study consent procedures

Consent Form

Persons designated to discuss and document consent

Select the names of persons designated to obtain consent/assent

[name], PHD

[name], MD

[name], PHD

Type in the name(s) not found in the above list

[name], MA

Study Procedures

Describe the procedures required for this study

As shown in the study overview flow chart below, the study comprises the following procedures: 1) eligibility assessment; 2) assessment visit; 3) treatment (during which there will a separate (additional) meeting with an IE at baseline and week 4); 4) end of treatment assessment; 5) follow up assessment (3 months after treatment end). As follows:

Flow Chart of Study Procedures

Visit 0: Eligibility Assessment	Visit 0.5: Assessment (and first MRI scan for eligible subjects)	Weeks 1-8: Once weekly Trauma- modified Equine- assisted therapy. These visits will last 90 minutes and take place at the equine facility.	Visit 8: End of treatment arm (and second MRI scan for eligible subjects)	Visit 10: 3 month follow up assessment

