	Clinical assessment, Informed Consent, SCID & CAPS 4 and CAPS-5, Patient Treatment Log MMSE for participants over 60 years of age, TBI ID for MRI subjects, EKG for MRI subjects over 60 years of age, Interview, self- report measures.	Informed consent, self-report measures. F or MRI subjects:1.25 hr scan	Between treatment visits 4 and 5 participants will complete self-ratings and IE will administer clinical ratings at NYSPI (CAPS-4 and CAPS-5, HAM-D 17, CGI, Patient Treatment Log)	Independent evaluator and self- ratings (1.5 hrs.) For MRI subjects:1.25 hr scan

Table 1. Flow Chart of Assessments for Study Participants

	Wk 0	Wk .5	Wk 1	Wk 2	Wk k	Wk 3	Wk 4	Wk 4.5	Wk 5	Wk 6	Wk 7	Wk 8	Wk 8.5	Wk 20
Clinical Assessment	x													
SCID		x												

HAM-D 17	x	x	x	x	x
LEC-5	x				
CAPS-4	x		x	x	x
MMSE	x				
TBI ID	x				
Informed Consent		x			
CAPS-5	x		x	x	x
Patient Treatment Log	x		x	x	x
ADC Demographics	x				
CVC Background Information Questionnaire		x			
CGI-severity	x	x	x	x	x
CGI-change	x	x	x	x	x
PCL-5	x		x		x
BDI	x	x		x	x
SAS		x		x	x
Q-LES-SF	x		x		x
SF-12	x		x		x
FAD	x				
M2C-Q	x				
CSQ-8		x	x		x
Credibility/Expectancy Q		x	x		x
POMS		x	x	x	x
CTQ		x			
GAD-7	x		x	x	x
CVC Suicide Risk Assessment and Screener	x		x		x
DRII-2	x				
VATBIST	x				
CAGE-AID	x				

4.A1. Preliminary Screening: Potential subjects will be screened by telephone by a research assistant after obtaining oral consent.

Eligibility Assessment: Potential participants deemed as likely study eligible following preliminary screening will sign the Anxiety Disorders Clinic informed written consent for the initial evaluation (IRB # 7049R) and undergo assessment as per the Columbia Veterans Research Center protocol (IRB#7218). As

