part of this protocol, an experienced clinician will evaluate presenting symptoms, psychiatric history, treatment history, medical history, military history, trauma history, social and family history, and current medical status. Participants will also complete a battery of self-report measures, including measures utilized by the Columbia Veterans Research Center as part of diagnostic and history assessment (30 minutes). In addition, a trained research team member will administer the Clinician-Administered PTSD scale (CAPS-4 and 5), structured clinical interview for DSM-5 (SCID), HAM-D 17, Patient Treatment Log, the TBI ID for subjects considering MRI participation, and the Mini Mental State Exam for participants over 60 years of age. An EKG will be administered to participants over the age of 60 who are considering MRI participation. These interviews will determine whether individuals meet inclusion criteria have been met. Finally, a urine sample will be collected from female subjects who appear to be eligible to participate in the MRI scans to test for pregnancy.

4.A2. MRI Scanning: For the MRI procedures, the subject will be instructed to lie as still as possible within the magnet for approximately 45 minutes. When we position a subject in the scanner, head movement will be minimized through: (a) instructions to the participant; and (b) packing the head inside the head coil with a system of foam padding and pillows that we have found is well-tolerated by the participants, yet limits movement. All precautions and protections will be given to the participant to ensure that they are as safe and comfortable as possible. For the participant's comfort within the scanner, they will lie on a padded table with a pillow to rest their heads on. A blanket will also be provided to keep subjects warm during the procedure.

fMRI Scan

For all subjects eligible to undergo fMRI scanning, there will be two fMRI sessions. MRI scans will be performed in the NYSPI 3.0T GE scanner. The scanning session will last approximately 45 minutes, with an additional 30 minutes total for set-up. subjects will have a urine pregnancy test on the day of the MRI scan, before being scanned. Thus, the fMRI session lasts about 1 hr and 15 minutes .

MRI Results

If the neuroimaging studies reveal significant deficit or an emergent and previously undiagnosed medical condition, this information will be discussed with the participants and transmitted to their physician.

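### The only itemised pretreatment CAPS-5 comes from the assessment that selects patients on CAPS-4, so regression to the mean is part of what the SAP calls a treatment effect

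*Combined protocol and SAP*

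**What the plan says.** **Selection and first rating.** Inclusion criterion 3 requires a "CAPS-4 score equal to or greater than 50". Section 4.A1 (Eligibility Assessment) says that "a trained research team member will administer the Clinician-Administered PTSD scale (CAPS-4 and 5"), along with other interviews, and that these interviews settle whether the inclusion criteria are met. The flow chart of study procedures lists both CAPS versions at Visit 0. For Visit 0.5 it lists "Informed consent, self-report measures" and the MRI scan, but no CAPS.

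**Who rates baseline.** The opening of Study Procedures announces a separate, additional "meeting with an IE at baseline and week 4". The Lay Summary lists Phase 2 evaluations at baseline, week 4, week 8 and "at three-month follow-up by independent evaluators". The flow chart assigns the midpoint and end-of-treatment ratings to an independent evaluator (IE).

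**Timing.** The section on research-related delay allows up to 6 weeks before study treatment for veterans not in treatment. It also admits veterans who are receiving treatment elsewhere.

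**Analysis.** The SAP describes the design as "In line with previous open-trial studies exploring novel psychotherapies for different psychopathologies" and plans an intent-to-treat analysis, "thereby enabling data analysis for all 63 patients". Under the label of treatment effects it plans a repeated-measures ANOVA over pretreatment, midpoint, posttreatment and follow-up, with Bonferroni post hoc comparisons. It adds: "All statistical tests will be 2-sided". It does not say which visit or rater supplies the pretreatment score, and it does not mention regression to the mean.

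**The concern.** Patients enter because their CAPS-4 is high on a given day. Part of a high score is temporary fluctuation and rating error, which will not recur in full at the next assessment. A CAPS-5 rated at the same assessment by the same person is likely to share some of that error. Its mean among those admitted is then too high as a reference, and later scores would fall somewhat without any therapy. The wait before session 1, and treatment received elsewhere, can add further change that the therapy did not cause.

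A control arm would show the same fall and cancel it. This trial has none, so the fall goes straight into the time effect, the effect size and every CAPS-5 contrast with pretreatment.

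**Working it through.** **1. Is there another pretreatment CAPS-5?**
- Section 4.A1 and the flow chart place it at Visit 0, and none is listed at Visit 0.5.
- Table 1 has lost its column alignment, but the CAPS-4 and CAPS-5 rows each carry four marks against five for the HAM-D. Four fits one pretreatment rating plus midpoint, end and follow-up.
- The section on minimizing risks separates intake from baseline and adds only the BDI-II at baseline.
- Against this, Study Procedures and the Lay Summary both place an IE at baseline, without saying that a CAPS was given there.

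The itemised schedule therefore shows one pretreatment CAPS-5, at selection, and the narrative conflicts with it.

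**2. How large could the artefact be?** The plan gives no SD, effect size or power figure, so there is nothing to reproduce. From the documents: n = 63; two-sided α = .05; four time points, hence 6 pairs and .05/6 = .0083 per comparison. The rest is assumed.

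The model is trivariate normal: CAPS-4 at screening, CAPS-5 at screening and CAPS-5 later, with no true change and selection at CAPS-4 ≥ c (in SDs from the referral mean).
- λ = φ(c)/(1 − Φ(c)), and v = 1 + cλ − λ² is the variance of CAPS-4 after selection.
- Expected CAPS-5 fall = (r_same − r_later) × λ, in referral SDs. These are the correlations of screening CAPS-4 with same-occasion and later CAPS-5.
- d = fall ÷ √(1 − r_same²(1 − v)), that is, in SDs of the selected sample at pretreatment.
- The CAPS-5 retest correlation is taken as r_later/r_same. The SD of change is √[2(1 − r_later/r_same) − (r_same − r_later)²(1 − v)].
- dz = fall ÷ SD of change. The chance of a significant fall comes from the noncentral t with 62 df and noncentrality dz√63.

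Worked case with c = −0.5, r_same = 0.90, r_later = 0.80:
- λ = 0.3521/0.6915 = 0.509 and v = 0.486.
- Fall = 0.10 × 0.509 = 0.051 (simulation gave 0.052).
- d = 0.051/0.764 = 0.067.
- dz = 0.051/0.466 = 0.109.
- Chance of a significant fall at .05 = 13%.

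The ranges below are over (r_same, r_later) = (0.90, 0.85), (0.90, 0.80), (0.90, 0.70) and (0.85, 0.60):

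| Cut-off relative to referral mean | Pass | d | Significant fall at .05 | At .0083 |
|---|---|---|---|---|
| 1 SD below | 84% | 0.02–0.08 | 5–11% | 1–3% |
| 0.5 SD below | 69% | 0.03–0.16 | 9–27% | 2–9% |
| At the mean | 50% | 0.06–0.27 | 15–56% | 4–29% |
| 0.5 SD above | 31% | 0.09–0.42 | 27–86% | 10–64% |

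These are chances of a significant fall only. Without the artefact they would be 2.5% and 0.4%, half of each two-sided level. The first three rows give the stated range; the fourth shows how steeply the answer depends on where 50 lies among those assessed. For scale, n = 63 gives 80% power for dz = 0.36 at .05 and 0.45 at .0083. The largest spurious dz in the first three rows is 0.27.

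**3. With a separate baseline rating.** If a post-eligibility rating correlates with the screening CAPS-4 no more strongly than later ratings do, the fall is (r_later − r_later) × λ = 0 and the nominal error rates return.

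**The case against.** The strongest reply is that this is an exploratory open pilot and that regression to the mean is a known limit of any such design with an entry threshold. That stands as context. It does not cover the SAP's wording, or the silence on which visit supplies the reference score.

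The schedule tables are damaged in extraction and cannot exclude an IE baseline CAPS-5. That stands too. If one was made and serves as the pretreatment score, most of the point falls away.

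Three stronger readings do not hold:
- **The rater changed from screening staff to an IE.** Section 4.A1 does not say that the team member is not an IE, and two other passages place an IE at baseline. If raters did differ systematically, by 0.1 to 0.3 SD with a retest correlation of 0.7 to 0.8, a significant fall at .05 would occur in 17 to 96% of trials with no true change. That is conditional on a difference the documents do not show.
- **All the efficacy evidence rests on this score.** The SAP also names the PCL-5, HDRS and BDI-II and designates none as primary. Two of these are self-reports, and the BDI-II is repeated at baseline.
- **A false-positive rate near one half is typical.** That belongs to the unfavourable end of assumed values.

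A new rating is not available as a remedy either. The continuation application reports that all interventions are complete and only analysis is ongoing. Midpoint-onward comparisons are no clean substitute. They are already among the planned post hoc tests, they omit change in the first half of treatment, and they follow possible removals for non-improvement at week 4 (section 4.A.6).

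**Conclusion.** The point holds for the CAPS-5. As itemised, its pretreatment score is taken at the selecting assessment, and the single-arm SAP counts the resulting regression to the mean as treatment effect. The direction favours the therapy. The size runs from trivial to moderate: d about 0.02 to 0.27, and a 5 to 56% chance of a significant fall at .05 with no true change.

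Those figures rest on normal scores, the four assumed correlation pairs and a cut-off from 1 SD below the referral mean to the mean. None of these is in the documents. The result also presumes that no separate IE baseline CAPS-5 supplies the pretreatment score, which the documents leave unresolved. A change of rater remains possible but not established.

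**What to change.** 1. Reconcile the Lay Summary and the opening of Study Procedures with the flow chart, Table 1 and section 4.A1. State who made each CAPS-5 rating and at which visit.
2. Define the pretreatment CAPS-5 in the SAP. If an IE rated it after eligibility and before session 1, use that rating and keep the eligibility CAPS for selection only.
3. If only the eligibility rating exists, add a sensitivity estimate: observed CAPS-5 change minus expected regression to the mean. Under the model above, the expected amount is r_same × (1 − retest reliability) × λ × the referral SD. Tabulate it for reliabilities 0.7 to 0.9 and several cut-off positions, with r_same stated. If the CAPS-4 scores of everyone assessed are held, they locate the cut-off directly.
4. Replace the treatment-effects wording with *within-group change over time*.
5. Cite the midpoint-onward contrasts only as supportive, with the two limits given above.

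The cost is a few lines of SAP text, a little more analysis and a slightly smaller reported CAPS-5 effect. No new data are needed.
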